# Laser Therapy protocol:

Mona Lisa Touch is a fractional CO2 LASER that has applications for treatment of the vulva and vagina. Patients randomized to this arm will undergo 3 treatments, 6 weeks apart. Patients will be advised to avoid any vaginal creams, lubricants or ointments, along with vaginal intercourse 48 hours prior to and 48 hours following LASER treatments.

Speculum examination will be performed and pH obtained. Any existing vaginal discharge will be removed prior to therapy. 2.5% lidocaine and 2.5% prilocaine will be applied to the external vulva for 30 minutes to 1 hour prior to procedure. This cream will be removed from the vulva prior to LASER application.

#### Internal treatments settings:

- First treatment: Power 30W, Dwell time 1000us, Spacing 1000um, Smart Stack 1
- Subsequent treatment: Power 30W, Dwell time 1000us, Spacing 1000um, Smart Stack 3

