# Methods

We propose a randomized controlled trial to evaluate the clinical difference between the LASER and topical vaginal estrogen in treating patients with rUTI. We expect to enroll 94 patients, to power this study to 80% with type I error of 5%, expecting a recurrence in UTI of 16% and non-inferior margin of 20%. This is accounting for a 10% drop out rate. While this clinical margin is wide, this project will provide us with ample data to apply for external funding, along with a wealth of microbiome data to evaluate in Aim 2. Menopausal women with rUTI will be recruited from the Departments of Urology and Gynecology. If they meet inclusion criteria, they will be randomized to treatment of topical vaginal estrogen or LASER therapy. LASER therapy will be applied 6 weeks apart for a total of 3 treatments. Topical vaginal estrogen will be prescribed per the patient's formulary and preference. Patients will be monitored for recurrence of culture positive UTI.

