### External treatments settings:

• Power 26W, Dwell time 800us, Spacing 800um, Smart Stack 1

Any deviation from these settings will be at the discretion of the provider performing the LASER therapy and will be documented in the patient's medical record.

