# **Data Collection**

Demographic information will be collected, which will include age, race, and comorbidities. Urinary cultures will be collected from prior to studies and subsequent to enrollment, with details of results documented. MESA questionnaire will be used to assess baseline and subsequent urinary symptoms to evaluate for change following the procedure as a secondary outcome. DIVA questionnaire will assess change to sexual function and symptoms of GSM at baseline and following treatment. All the data will be collected and entered in the REDcap database.

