# **Recurrent UTI**

Our goal is to test the hypothesis that LASER treatment is non-inferior to vaginal estrogen in rUTI patients. If LASER is found to be effective, it would offer clinicians a modality of treatment for these patients that avoids antibiotics and hormone

replacement. It would also offer hope to patients for whom hormones are contraindicated.

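### Neither visit schedule, Data Collection nor Statistical Analysis provides for structured collection or comparison of adverse events, tolerability or reasons for stopping

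*Combined protocol and SAP*

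**What the plan says.** All references are to the combined protocol and SAP.

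- **Treatment.** Laser Therapy protocol: "Patients randomized to this arm will undergo 3 treatments, 6 weeks apart". Internal treatments settings give "First treatment: Power 30W, Dwell time 1000us, Spacing 1000um, Smart Stack 1" and then "Subsequent treatment: Power 30W, Dwell time 1000us, Spacing 1000um, Smart Stack 3". External treatments settings send departures to the chart: "Any deviation from these settings will be at the discretion of the provider performing the LASER therapy and will be documented in the patient's medical" (quote cut before its last word).
- **Schedules.** The estrogen table (under Vaginal Estrogen Protocol) and the LASER table have the same six rows: consent, vaginal pH, vaginal swab, urine, MESA and DIVA. At the first, second and third LASER treatment visits only the pH row is marked. The month-6 column in both tables depends on the funding period.
- **Data Collection.** "Demographic information will be collected, which will include age, race, and comorbidities". The section then adds urine cultures and the two questionnaires, all held in REDCap.
- **Statistical Analysis.** It covers UTI prevalence, recurrence rate and time to first recurrence, and MESA, DIVA and vaginal histology over time.
- **Intended use of the result.** Recurrent UTI: "If LASER is found to be effective, it would offer clinicians a modality of treatment for these patients". No safety condition is attached.

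**The concern.** The trial compares a procedure with a vaginal cream, so the two arms may differ in kind as well as frequency of unwanted effects. A reader of the final report will want to know what happened to women at and after the sessions, and why any of them stopped. If the plan is followed exactly, no form asks, and an analyst cannot recover afterwards what was never recorded.

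Two features add to this. Setting deviations may be the only trace of a poorly tolerated session, and they are kept outside the study database. The plan also allows for 10% drop-out but asks for no reason, so a woman who leaves because of treatment may not be distinguishable in the trial data from one who leaves for another cause.

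**Working it through.** **Step 1: where harm data could enter.**

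| Place in the plan | What is provided | Adverse events, tolerability or reason for stopping |
|---|---|---|
| Estrogen schedule | consent, pH, swab, urine, MESA, DIVA | none |
| LASER schedule, three treatment visits | pH | none |
| LASER schedule, baseline and months 4 and 6 | pH, swab, urine, MESA, DIVA (consent at baseline) | none |
| External treatments settings | deviations, in the medical record | no research data item, no reason asked for |
| Data Collection | demographics, comorbidities, cultures, MESA, DIVA | none |
| Statistical Analysis | UTI outcomes, MESA, DIVA, histology | none |

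After baseline the questionnaires are first repeated at month 4, about one month after the third session at 3 months. The estrogen arm has no scheduled visit between baseline and month 4.

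**Step 2: the plan's own sample size.** Methods states "We expect to enroll 94 patients, to power this study to 80% with type I error of 5" per cent, "expecting a recurrence in UTI of 16% and non-inferior margin of 20" per cent, with 10% drop-out. Take 16% in both arms, 1:1 allocation (not stated) and a one-sided 5% level (sidedness not stated):

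n per arm = 2 × 0.16 × 0.84 × (1.645 + 0.842)² / 0.20² ≈ 41.6, rounded up to 42.

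The total is 84, and 84 / 0.90 = 93.3, rounded up to 94, or 47 per arm. The stated figure is reproduced. Collecting adverse events does not change it.

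**Step 3: what collection could show at this size.** If no event of a given type is seen in n women, the one-sided 95% upper bound is 1 − 0.05^(1/n).

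- n = 47: 1 − 0.05^(1/47) = 6.2%
- n = 42: 1 − 0.05^(1/42) = 6.9%

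The chance of seeing at least one event is 1 − (1 − p)^n. The documents give no event rate, so the values of p are assumptions:

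| True rate p | 47 women | 42 women |
|---|---|---|
| 1% | 38% | 34% |
| 2% | 61% | 57% |
| 5% | 91% | 88% |
| 10% | 99% | 99% |

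Harms affecting 5% or more of women would probably appear at least once, while rarer ones could easily be missed. Without systematic collection none of these statements can be made.

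**The case against.** The strongest reply is that the plan is not blind to harm. Background describes GSM as including burning, irritation, dysuria and pain on intercourse, which overlap with plausible local effects of a vaginal procedure. DIVA covers GSM symptoms and sexual function, and MESA covers urinary symptoms. Both are taken in both arms and compared over time by mixed models. The LASER procedure includes a speculum examination, and deviations are charted.

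Much of this stands, so a reader who infers that the trial will have no harm data at all goes too far. It does not close the gap. As described, the questionnaires do not record events, severity, acute effects around a session or reasons for stopping. The speculum examination has no data item apart from pH. Histology is named in the analysis, but neither schedule lists a biopsy.

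A reader might also infer that the change from Smart Stack 1 to Smart Stack 3 is itself an error, or that it multiplies the delivered energy by a known factor. The documents support neither. The settings are stated once and consistently, and Smart Stack is not defined, so no energy figure can be derived. The gap would be the same with no step between sessions.

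Finally, the front pages and consent text are not available, so wording on risks or safety reporting there cannot be excluded. The schedules, Data Collection and Statistical Analysis are available, and they are where such items would have to appear to yield comparative data.

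**Conclusion.** The point holds as a gap in planned data. In neither arm does the plan provide structured collection or analysis of adverse events, procedural tolerability or reasons for discontinuation. Symptom worsening could be seen by arm at month 4, and at month 6 only if that visit takes place. The trial could meet its non-inferiority aim and offer LASER as a treatment option without a planned comparison of harms.

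The gain from closing the gap is real but limited. It rests on 42 to 47 women per arm, assuming 1:1 allocation, and at that size only common harms can be characterised. The non-inferiority test and the sample size are unaffected. No view is taken on the LASER settings or on the step between sessions.

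**What to change.** 1. Add one row, adverse events, tolerability and reason for discontinuation, to both schedules. Use the same fixed questions in both arms at month 4, and at month 6 if that visit is held.
2. Use the same form at LASER sessions 2 and 3, as a record only. Effects of sessions 1 and 2 are then asked about at the next session, and those of session 3 at month 4.
3. Enter the form in REDCap, together with any deviation from the settings and its reason.
4. In Statistical Analysis, add a descriptive by-arm table of events and discontinuations. Base the between-arm comparison on the visits common to both arms, because the LASER arm is asked more often. Show the LASER session data separately.

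The cost is one form, one table and a few minutes of coordinator time per visit. No visits are added and the sample size stays at 94. The report should say that rarer harms are beyond the trial's reach. No change to treatment settings or clinical rules is implied.

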### External treatments settings:

• Power 26W, Dwell time 800us, Spacing 800um, Smart Stack 1

Any deviation from these settings will be at the discretion of the provider performing the LASER therapy and will be documented in the patient's medical record.

# Vaginal Estrogen Protocol

Women randomized to vaginal estrogen therapy will be offered vaginal cream. Two FDA approved formulations exist and patients will be offered the choice between the two, which may also be dependent on their insurance formulary preference.

- 1. Conjugated estrogen (Premarin): 0.5 gm per vagina twice weekly
- 2. Estradiol (Estrace): 1gm per vaginal twice weekly

**Specific Aim 1:** Evaluate the number of culture positive, symptomatic UTI in women following randomization to vaginal estrogen and vaginal LASER therapy.

Methods: Following randomization and treatment initiation, patients will be monitored for recurrence of UTI. Patients will be encouraged to call the treating physician for treatment antibiotics according clinical judgment. Standard urine cultures will be obtained along with information about what type of antibiotic treatment was administered. Validated questionnaires will also be collected to monitor symptoms of GSM and also of urinary incontinence symptoms (Appendix A and B). Patients will be followed for 6 months with evaluations at baseline, 4 months, and 6 months.

**Specific Aim 2:** Characterize the urinary and vaginal microbiome at baseline and at 4 months of patients in each group.

Methods: Baseline vaginal and catheterized urine samples will be collected along with samples at 4 months. Standard catheterized urine cultures will be performed and if symptomatic, treated appropriately (per Aim 1). Microbiome of urine and vaginal environments will then be analyzed using 16S ribosomal DNA sequencing along with shotgun metagenomics. For this study, we will perform sequencing and metagenomics on the first 16 patients in each arm (32 patients total). The remaining collection will be biobanked for future analysis. These techniques will allow us to measure the abundance of different bacteria, but also evaluate the genetic variation and evolutionary effect from treatment. This will also allow us to evaluate for the differences in the microbiome between responders and non-responders in each treatment arm, considering factors such as UTI, symptoms, pH, etc.

Vaginal Estrogen arm	Baseline	4 months	6 months (if can be completed within the funding period)
Informed consent	X		
Vaginal pH	X	X	Х
Vaginal swab collection	X	X	X (banked)
Urine collection	Х	Х	X (banked)
MESA questionnaire	X	Х	Х
DIVA questionnaire	Х	Х	X

# Inclusion Criteria:

- Female patient >18 years old
- Postmenopausal status, documented by prior bilateral salpingooophorectomy, or absence of menses >12 months
- Recurrent urinary tract infections as defined by 3 culture positive urine cultures in the last 12 months, or 2 positive urine cultures in the last 6 months.
  - Positive urine cultures defined by >100K colony forming units of 1 or 2 bacterial species on clean catch sample, or >1000 colony forming units of 1 or 2 bacterial species on sample via straight catheterization.
- Patients on vaginal estrogen must undergo a 1 month washout period prior to initiation of the trial.

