Fractional CO2 LASER vaginal therapy has recently been studied for the treatment of GSM. LASER therapy is currently commercially available and has FDA clearance for use in gynecology. Current evidence shows that with treatment, histologic changes of the vaginal epithelium have shown regeneration to a premenopausal state, along with subjective improvement in GSM symptoms and sexual function. Using LASER therapy, Zerbinati et al described response by the vaginal epithelium with thickening, superficial shedding and renewing of stratified epithelium, which was maintained 2 months after treatment.[4] Athanasiou et al also described the impact of LASER therapy on the vaginal flora, decreasing the vaginal pH to 4.7 (p<0.001) and increasing the Lactobacillus colonies from 30% to 79%.[5] Based on the impact this promising new regenerative therapy has on the vaginal epithelium and microbiome, we anticipate this may have a positive impact on women with rUTI.

- We therefore hypothesize that fractional CO2 LASER vaginal therapy is non-inferior to topical vaginal estrogen therapy for the treatment of rUTI.
  a. Primary Outcome: Improvement in recurrence of culture positive UTI
- 2. We also hypothesize that LASER therapy will improve the urinary and vaginal microbiome, decreasing the uropathogenic presence and increasing Lactobacillus.
  - a. Measurement 1: The number of UTI with UPEC isolated from patients
  - b. Measurement 2: The pH of the vagina as a proxy for presence of Lactobacillus sp.
  - c. Measurement 3: Categorize vaginal and urinary microbial communities

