### Exclusion Criteria:

- Hematuria without appropriate workup
- Pelvic organ prolapse beyond the hymen
- Clinically relevant urinary retention
- Pelvic reconstructive surgery within 6 months
- Reconstructive pelvic surgery with "mesh kits"
- Clinically relevant nephrolithiasis
- History of breast cancer
- Contraindication to topical estrogen therapy
- Anticoagulation therapy
- Prior pelvic or vaginal radiation therapy
- Prior gynecologic malignancy
- Undiagnosed genital bleeding

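### Vaginal estrogen is washed out, but the plan has no rule for prior vaginal LASER and records neither prior LASER nor current systemic estrogen

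*Combined protocol and SAP*

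**What the plan says.** The only prior-treatment rule is in the Inclusion Criteria: "Patients on vaginal estrogen must undergo a 1 month washout period prior to initiation of the trial". The Exclusion Criteria have twelve items. The one that concerns estrogen use directly is "Contraindication to topical estrogen therapy", which does not cover a woman already taking oral or transdermal estrogen. No item mentions earlier vaginal LASER.

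The Background says that "LASER therapy is currently commercially available and has FDA clearance for use in gynecology" and reports an epithelial response to it: "thickening, superficial shedding and renewing of stratified epithelium, which was maintained 2 months after treatment".

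In the LASER arm, the only restriction on vaginal products is short and tied to each session: "Patients will be advised to avoid any vaginal creams, lubricants or ointments, along with vaginal intercourse 48 hours prior to and 48 hours following LASER".

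No later section closes the gap. Subject Randomization uses blocks of 6 and names no stratification factor. Data Collection names age, race and comorbidities, prior and later urine cultures, and the two questionnaires. Statistical Analysis has no covariate adjustment or sensitivity analysis for earlier or background treatment.

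The hypothesis is that "fractional CO2 LASER vaginal therapy is non-inferior to topical vaginal estrogen therapy for the treatment of rUTI". The Recurrent UTI section adds that, if LASER is effective, "it would offer clinicians a modality of treatment for these patients that avoids antibiotics and hormone" replacement.

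**The concern.** By requiring an estrogen washout, the plan accepts that earlier treatment can carry into follow-up. It applies that reasoning to one of its two treatments. On its own account the other is commercially available and has an effect lasting at least 2 months, against a follow-up of 6 months. Three kinds of women can therefore enter:

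- a woman with a recent LASER course, randomized to estrogen and followed under both;
- a woman whose qualifying infections came after a LASER course, randomized to LASER again;
- a woman on systemic estrogen, randomized to LASER and followed under LASER plus hormones.

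At stake are how cleanly the UTI comparison can be read, the baseline for Aim 2, and how far a LASER result could support a statement about avoiding hormones. Because neither exposure is named for collection, the planned data would not allow a later check.

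**Working it through.** **Inputs.** From Methods: N = 94, power 80%, type I error 5%, expected recurrence 16%, margin 20%, dropout 10%. Assumed: equal allocation, a margin in absolute points, and a one-sided 5% test; the documents state none of these. The share of exposed women and the effect of either exposure on UTI are not given, so ranges are used.

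**The plan's own N.** Per arm, n = (1.645 + 0.842)² × 2 × 0.16 × 0.84 / 0.20² = 41.6, rounded up to 42. The total is 84, and 84 / 0.90 = 93.3, rounded up to 94. This matches. A one-sided 2.5% test gives 53 per arm and 118 in total, which does not match. The one-sided 5% test is therefore used below. It is inferred from the sample size, since Statistical Analysis names only a chi-square or Fisher's test for the proportions.

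**Formula.** P(declare non-inferiority) = Φ[(0.20 − (pL − pE)) / SE − 1.645], with SE = √{[pE(1 − pE) + pL(1 − pL)] / 42}. With pE = pL = 0.16 this gives 80% power. With LASER exactly at the margin (pE = 0.16, pL = 0.36) it gives 5.0%.

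**A. Systemic estrogen in the LASER arm.** Assume it brings the risk of exposed women down to 16%, and adds nothing for women already on vaginal estrogen. Then pL = 0.36 − 0.20f for exposed share f. At f = 10%, pL = 0.34, SE = 0.0924, and Φ(0.02/0.0924 − 1.645) = Φ(−1.43) = 7.7%.

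| Exposed share | 5% | 10% | 20% | 30% |
|---|---|---|---|---|
| Observed difference (points) | 19 | 18 | 16 | 14 |
| False non-inferiority | 6.2% | 7.7% | 11.4% | 16.3% |

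**B. Residual LASER in the estrogen arm.** Assume it halves the risk of exposed women in that arm and adds nothing in the LASER arm. Then pE = 0.16 × (1 − 0.5f). At f = 10%, pE = 0.152, the difference is 20.8 points, and Φ(−0.008/0.0925 − 1.645) = 4.2%. Power is for pL = 0.16.

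| Exposed share | 5% | 10% | 20% | 30% |
|---|---|---|---|---|
| False non-inferiority | 4.6% | 4.2% | 3.4% | 2.8% |
| Power | 79% | 78% | 76% | 74% |

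**C. An exposure that lowers risk by the same ratio in both arms.** With a risk ratio of 0.5, both rates are multiplied by 1 − 0.5f. False non-inferiority is 5.6%, 6.2%, 7.7% and 9.6% at 5%, 10%, 20% and 30% exposed. This is the one pattern examined here in which prior LASER would push towards non-inferiority.

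**Aim 2.** The Background cites LASER as lowering vaginal pH to 4.7 and raising Lactobacillus from 30% to 79%, variables that Aim 2 follows. Sequencing covers the first 16 women per arm, so two recently treated women would be 2/16 = 12.5% of an arm with an already shifted baseline.

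**The case against.** **Direction of bias.** A reader might infer that both exposures make the arms more alike and so favour non-inferiority. The documents do not support that for prior LASER. In the estrogen arm a residual LASER effect is added to the control treatment rather than replacing it. The comparator gets better or stays the same, as calculation B shows. A woman whose infections followed LASER may be a non-responder, which also works against the LASER arm. Only the proportional pattern in C reverses this, and nothing in the documents points to it. The 7.7% and 11.4% figures therefore must not be attached to prior LASER.

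**Systemic estrogen.** The Background reports UTI prevention for vaginal estrogen only, and no section says that oral or transdermal estrogen prevents UTI. Long-standing users would have met the recurrence criterion despite their treatment. This stands: calculation A is conditional and illustrative. Admitting such women is also a defensible pragmatic choice, since the comparator is vaginal estrogen.

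**Randomization.** Both exposures are balanced in expectation. This stands, and it rules out confounding. It does not rule out dilution or effect modification.

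**Aim 2.** A stable background hormone is present at baseline and at 4 months, so it does not by itself create a false change. This stands. The Aim 2 concern is limited to recent LASER, whose effect may be in place at baseline.

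**The hormone statement.** A reader might take the Recurrent UTI section as a planned conclusion. It is conditional motivation, not an estimand. What remains is that any such statement in the report would need support from women not taking systemic estrogen.

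**Conclusion.** The omission is certain; its size is unknown. The plan has no eligibility or washout rule for prior vaginal LASER, and names neither that exposure nor systemic estrogen among its data. As written, it can admit women who carry the test treatment, and the planned data would not identify them.

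The likely consequence of prior LASER is a modest loss of power (80% to 78% at 10% exposed, under a halved risk), a mixture of first courses and retreatments, and a blurred Aim 2 baseline. A false non-inferiority finding is a concern only for systemic estrogen in the LASER arm, and only if it protects as vaginal estrogen does: 7.7% at 10% exposed and 11.4% at 20%, against a nominal 5%.

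This is a cheap improvement, not a flaw that invalidates the comparison. The documents do not support the stronger readings that the trial is biased towards non-inferiority by both routes, or that systemic-estrogen users must be excluded.

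**What to change.** 1. **Exclusion Criteria:** add prior vaginal LASER treatment. If a time window is used, the sponsor should choose and justify it. The only persistence figure in the documents is 2 months, and it concerns epithelium rather than UTI.
2. **Data Collection:** add baseline REDCap fields for prior vaginal LASER (ever, and date) and current systemic estrogen.
3. **Statistical Analysis:** pre-specify one sensitivity analysis that repeats the UTI comparison without women on systemic estrogen at baseline. Selection on a baseline variable keeps the comparison randomized. Any statement that LASER avoids hormones should rest on this analysis as well.

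**Cost.** One criterion, one or two data fields and one extra analysis; N stays at 94. A few eligible women are lost. If Subject Recruitment means a third of about 200 women a year, 2 years yield about 2 × 200/3 = 133, against 94 needed, so there is room. The sensitivity analysis is supportive only: dropping 10% of 84 evaluable women leaves 37.8 per arm, and Φ(0.20/√(0.2688/37.8) − 1.645) = 77% power; dropping 20% leaves 33.6 per arm and 72%.
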